5.3 Changes to the study objectives during the course of the study

These details differ slightly from those in the protocol (version 6, 21 March 2012):

STATISTICAL ANALYSIS PLAN

COPTIC: Coagulation and platelet laboratory testing in cardiac surgery
A prognostic study of associations between post-operative test results and subsequent bleeding

- In the protocol, all outcomes are defined as clinical outcomes, with no differentiation between primary and secondary outcomes.
- The definition of CCB detailed in the protocol includes the statement that the intervention took place before carrying out a Thromboelastogram (TEG) analysis, or requesting a TEG analysis. This has now been removed from the definition of CCB at the agreement of the clinical investigators (GJM and AM).
- Clinical decision to return to theatre because of suspected bleeding has been added to the definition of CCB.
- The interval defined for red cell transfusion was defined in the protocol as during hospital stay; these data are available for CICU admission only. No details were recorded in the protocol in relation to the early pro-haemostatic treatments; these data are also available for CICU admission only.
- The serious post-operative complications detailed in the protocol (secondary outcomes iii) were “death, myocardial infarction, permanent stroke, renal failure (new requirement for dialysis) and sepsis”. These have been amended to “death, myocardial infarction, **any stroke, acute kidney injury (AKI)** and sepsis”. AKI will be defined using a modified KDIGO AKI Work Group laboratory definition⁵; AKI is present if serum creatinine increases by $\geq 26.5 \mu\text{mol/l}$ from the pre-operative value within 48 hours of surgery OR serum creatinine increases ≥ 1.5 times the pre-operative value within 7 days of surgery. The decision to replace “renal failure (new requirement for dialysis)” with AKI using creatinine data was made in the light of the amount of missing information in PATS.

6. DERIVATIONS

6.1 Primary endpoint

The rules and data sources for the primary endpoint of CCB are as follows:

New variable	Rules	Data sources
CCB (binary)	If post-operative blood loss 6hrs post CICU admission > 600mL OR intervention with a pro-haemostatic treatment (see section 5.1 for the definition) during interval 2 [interval 1 or interval 2b for therapeutic protamine] OR reoperation for bleeding where no surgical cause for bleeding is identified.	CRFs (blood loss data) PATS (return to theatre due to suspected bleeding) INNOVIAN clinical information system and CRFs (transfusion data) PATS (rFVII) Haematology Department (rFVII and fibrinogen concentrate)

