2.2 Overview of COPTIC study design

COPTIC is a prospective observational study of patients undergoing cardiac surgery at the Bristol Heart Institute.

- i. All participants undergo standard pre-operative, anaesthetic, surgical and post-operative care according to existing protocols.
- ii. Blood samples are obtained in the operating theatre at the following time-points:

STATISTICAL ANALYSIS PLAN

[figure not shown]
COPTIC: Coagulation and platelet laboratory testing in cardiac surgery
A prognostic study of associations between post-operative test results and subsequent bleeding

- a. Immediately before induction of anaesthesia (*pre-operative sample; 9.5mls*)
- b. Immediately after reversal of heparin anticoagulation (*post-operative sample; 18.5mls*)

Data are collected until 12 hours after admission to Cardiac intensive care unit (CICU). The study timings are shown in Figure 1.

Figure 1: Timeline for COPTIC study

T0: time of pre-op sample

T1: cessation of CPB

T2: administration of final routine dose of protamine

T3: time of post-op sample

T4: time of arrival in CICU

T5: 6 hours after arrival in CICU

T6: 12 hours after arrival in CICU

T7: CICU discharge

Interval 1 time interval between pre-op and post-op samples [T3-T0]

Interval 2a post-op sample to 6 hours after admission to CICU [T5-T3]

Interval 2b post-op sample to 12 hours after admission to CICU [T6-T3]

Interval 2 time interval between post-op sample and CICU discharge [T7-T3]

This SAP refers to the analysis of post-operative Multiplate test results, ROTEM test results and TEG test results (part of Study B). A separate analysis plan will be written for the analyses of the other laboratory results from post-operative samples (also Study B).

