5. DEFINITIONS

5.1 Clinical concern about bleeding

The main objective of this prognostic study is to estimate how well test results from the post-operative blood samples predict CCB, i.e. bleeding that is likely to cause direct patient harm or indirect patient harm by precipitating a non-routine pro-haemostatic treatment or re-operation for bleeding for which no direct surgical cause is identified.

A participant will be classified as having experienced the primary outcome of CCB if any of the three circumstances below is documented within the designated time interval:

- i. Post-operative blood loss (volume collected through chest drain) greater than 600mL at T5¹ (interval 2a).
- ii. Intervention with a non-routine early pro-haemostatic treatment (EPT) defined as additional protamine after initial heparin reversal during interval 2b², fresh frozen plasma (FFP), cryoprecipitate, platelets, anti-fibrinolytic drug, recombinant human coagulation factors VII [rFVII] or fibrinogen concentrate during interval 2b (T3-T6 ; Figure 1).

¹ Chest drain volume after 6 hours from admission to CICU is likely to be an unreliable marker of actual bleeding because of contamination with tissue fluid. There is no universally effective threshold for clinical concern about post-operative bleeding even at T5, so 600 ml total during this interval is a pragmatic clinical suggestion. Chest drain volumes at T6 will continue to be collected but it is very difficult to suggest a plausible 'threshold' value at this time point that will reflect 'actual bleeding'.

² Medical notes and details for those patients who only received additional doses of protamine and no other non-RBC products will be reviewed. Those with only one dose of protamine, administered after the post-operative sample is collected but prior to admission to CICU will be considered "routine" administration of protamine. The medical notes for all other instances will be reviewed and the protamine will be classified as "routine" or "therapeutic" as appropriate. Those considered to have received "routine" dose(s) of protamine will not be included in the definition of EPT.

STATISTICAL ANALYSIS PLAN

COPTIC: Coagulation and platelet laboratory testing in cardiac surgery
A prognostic study of associations between post-operative test results and subsequent bleeding

- iii. Reoperation for bleeding recorded during hospital stay and failure to demonstrate a surgical cause for bleeding³.

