5.2 Secondary endpoint definitions

- i. Red cell transfusion expressed as: (i) any vs. none; (ii) total number of units transfused;(iii) >4 units vs. ≤4 units⁴ occurring intra-operatively or during CICU stay (interval 2).
- ii. Non-routine pro-haemostatic treatments (see [section 5.1](#) for definition), occurring in interval 2, and expressed as: (i) any vs. none and (ii) total number of units or dose administered.
- iii. Serious post-operative complications, i.e. death, myocardial infarction (MI), any stroke, acute kidney injury (AKI) and sepsis during hospital admission.

Secondary endpoints i) and ii) will be extracted from INNOVIAN and will cover the period of CICU admission, with information on therapeutic protamine for the time interval 2b extracted from the CRFs (time from the post-operative sample to 12 hours post-CICU admission). Secondary endpoints detailed in iii) will be extracted from the PATS Database or INNOVIAN. Due to known limitations in the completeness of the PATS database for some of these data, INNOVIAN data will also be utilised to identify these outcomes; firstly by the event being recorded in INNOVIAN and secondly by an electronic review of the following five free text fields extracted from INNOVIAN:

- Intensivists Review
- Problems (Physician Daily Review and Plan)
- Progress note (Physician Daily Review and Plan)
- Surgical Review
- CICU Ward round
- Plan of care on discharge

The search terms to be used are as follows:

	Innovian search terms	Context terms
Death	n/a (all captured in PATS/NHS Strategic Tracing Service [NSTS])	
Myocardial Infarction	Myocardial infarction Infarct	Q wave MI/myocardial infarction Non-Q wave MI/myocardial infarction

³ In order to account for reoperations which were conducted due to surgical cause of bleeding, relevant electronic notes for all patients who required a reoperation will be reviewed by a cardiac surgeon (GJM). Any patient identification details will be masked. Those who, in the opinion of the surgeon, had a surgical cause of bleeding will be excluded from the definition of CCB.

⁴ RBC transfusion of 1-2 units may occur at any time during or after surgery, usually in response to low haematocrit for which bleeding is only one cause. Thus, the number of red cell units transfused reflects poorly the extent of bleeding. However, larger volume RBC transfusions (arbitrarily defined as >4 units) more reliably reflect clinically important bleeding.

STATISTICAL ANALYSIS PLAN

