6.2 Secondary endpoints

New variable	Rules	Data sources
RBC transfusion	Any RBC transfusion during interval 2	INNOVIAN clinical information

⁵ Diagnosis, evaluation, and management of acute kidney injury: a KDIGO summary (Part 1). Kellum *et al.* Critical Care 2013, 17:204

STATISTICAL ANALYSIS PLAN

COPTIC: Coagulation and platelet laboratory testing in cardiac surgery
A prognostic study of associations between post-operative test results and subsequent bleeding

New variable	Rules	Data sources
(binary)	(the time between post-operative samples are taken and discharge from CICU).	system
RBC >4 units (binary)	Any RBC transfusion >4 units during interval 2 (the time between post-operative samples are taken and discharge from CICU).	INNOVIAN clinical information system
Non-routine pro-haemostatic treatments (binary)	Any platelet, FFP, cryoprecipitate or rFVII transfusion during intervals 1 and 2 (the time between post-operative samples are taken and discharge from CICU), or therapeutic protamine during interval 2b (the time between post-operative samples are taken and 12 hours post CICU-admission).	INNOVIAN clinical information system and CRFs
Serious post-operative complications:		
Death (binary)	Vital status (alive vs. died in theatre OR died in hospital).	PATS Database (updated with NSTS data)
MI (binary)	Any MI occurring before discharge OR death from MI in hospital.	PATS Database, INNOVIAN clinical information system and death certificate data
Stroke (binary)	Any peri- OR post-operative neurological complication (stroke; transient ischaemic attack; hemiplegia; paralysis; paraplegia; dysphasia; cerebral/CNS infarct/embolus).	PATS Database, INNOVIAN clinical information system
AKI (binary)	Serum creatinine increased by ≥ 26.5 $\mu\text{mol/l}$ from the pre-operative value within 48 hours of surgery OR serum creatinine increased ≥ 1.5 times the pre-operative value within 7 days of surgery.	Creatinine data
Infection during hospital admission (binary)	Any infective complication (chest infection; wound infection; mediastinitis; graft site infection; sternal wound infection; urinary tract infection; septic; sepsis; blood borne infection).	PATS Database and INNOVIAN clinical information system

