7.2 Specific analysis procedure

The approach is to evaluate the separate platforms (Multiplate/preop; ROTEM; TEG; Multiplate/postop) individually in the first instance, and then evaluate whether the inclusion of additional platforms would improve this. The reason for considering groups of variables by platform (rather than simply choosing the 'best' subset of variables) is because there is no cost of using extra variables from one platform, but an extra cost of doing a second test. The specific steps are as follows:

- Step 1 Review the prediction achieved by patient characteristics. Define an optimal model based only on "baseline" covariates⁶. There will be a separate model for
- **any CCB** (intra-operative or post-operative) and
 - **post-op CCB** only
- Comment: We expect these models to be consistent with one another, not least because the majority of events (post-op CCPB events) will be common to both models.*
- Step 2 Review of each test platform to obtain the best model for each, including the baseline covariates:
- pre-operative Multiplate in relation to **any CCB** (this model is interesting in its own right, but from a slightly different perspective, i.e. it allows the care team to make a plan to mitigate the risk of CCB or to prepare to manage it)
 - pre-operative Multiplate in relation to **post-op CCB**
 - post-operative Multiplate in relation to **post-op CCB**
 - post-operative ROTEM in relation to **post-op CCB**
 - post-operative TEG in relation to **post-op CCB**
- Comment: Each of these models will consider all variables for the test/timepoint, i.e. consider the test/timepoint as a "package." The first model stands alone for **any CCB**. For **post-op CCB**, this step will identify which of the latter four models is the best platform for predicting CCB, i.e. provides the best prediction. We hypothesise that the best platform will be one of the post-op platforms because the information from these is more 'proximal' to the outcome for these models, i.e. **post-op CCB**.*
- For the best test/timepoint** (assuming there is one best test), we will also investigate whether a model using test variables that are available early (for the test identified as best) performs as well as a model using the standard test variables available at "test completion."

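### Sections 5.1 and 6.1 give incompatible treatment windows for the primary outcome CCB, and the two CCB outcomes modelled in 7.2 are never derived

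*SAP*

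**What the plan says.** Section 2.2 of the SAP fixes the time scale: "Interval 1 time interval between pre-op and post-op samples [T3-T0"]; "Interval 2b post-op sample to 12 hours after admission to CICU [T6-T3"]; "Interval 2 time interval between post-op sample and CICU discharge [T7-T3"]. Interval 1 therefore ends at the post-operative sample, and intervals 2b and 2 both start there.

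Section 5.1 defines CCB. Its treatment criterion ties additional protamine to interval 2b and closes the product list with "fibrinogen concentrate during interval 2b (T3-T6 ; Figure 1"). Section 6.1 refers back to 5.1 for what counts as treatment, but sets the window as "during interval 2 [interval 1 or interval 2b for therapeutic protamine"].

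Section 7.2 asks for separate models for *any CCB*, explained as "intra-operative or post-operative", and for *post-op CCB* only. Models 2B to 2E use post-op CCB; Model 2A uses any CCB. Objectives A1(b) and A1(c) in section 7, and section 7.4.3, use CCB without qualification.

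For the secondary endpoint of pro-haemostatic treatment, section 6.2 counts any platelet, FFP, cryoprecipitate or "rFVII transfusion during intervals 1 and 2 (the time between post-operative samples are taken and discharge from CICU"). Section 5.2 states that its red-cell and pro-haemostatic endpoints "will be extracted from INNOVIAN and will cover the period of CICU admission", with therapeutic protamine taken from the CRFs.

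**The concern.** The study asks whether the sample at T3 predicts bleeding that follows it. An outcome rule that reaches back before T3 can count as predicted something that had already happened. A rule that runs on to CICU discharge counts treatment outside the 12 hours that the definition allows. Section 6.1 is the rule a programmer would code, and it does both.

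The component in dispute is not marginal. Section 7.4.6 reports that a large proportion of patients classified as CCB had neither excess drainage nor a reoperation and qualified through pro-haemostatic treatment. The window for that treatment therefore bears on the event rate, on every odds ratio and ROC curve for CCB, and on the sensitivity analyses in 7.4.6 and 7.4.7. With two windows in the plan, the choice between them could also be made after the data are seen.

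**Working it through.** No sample size, power or event figure is involved, so the check sets the sections side by side.

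**Step 1: CCB window by component.**

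| Component | Section 5.1 | Section 6.1 | Difference |
|---|---|---|---|
| Chest drain loss over 600 mL | T5 (6 h after CICU arrival) | same | none |
| Products (FFP, platelets and so on) | T3 to T6 | T3 to T7 | T6 to T7 added |
| Therapeutic protamine | T3 to T6 | T0 to T3, or T3 to T6 | T0 to T3 added |
| Reoperation, no surgical cause | hospital stay | no window given | 6.1 silent |

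Both treatment rows conflict.

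**Step 2: size of the added product window.** Excess = T7 − T6 = CICU stay − 12 h. The SAP gives no CICU length of stay. Assuming 24, 48 or 72 h, the excess is 24 − 12 = 12 h, 48 − 12 = 36 h or 72 − 12 = 60 h.

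**Step 3: where pre-sample protamine can enter.**
- Model 2A and the baseline model for any CCB: a pre-operative predictor or baseline covariates come first, so an interval 1 event follows them. No ordering problem.
- Models 2C to 2E: the outcome is post-op CCB, which is evidently meant to leave out earlier events. Section 6 has no rule for it, so the exclusion depends on the programmer. The boundary is also unstated: the sample is drawn in theatre, so *post-op* could start at T3 or at T4.
- A1(b), A1(c) and 7.4.3: the outcome is plain CCB. A1(b) points to 5.1, which has no pre-sample treatment, but the only coded variable is the one in 6.1, which has.

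**Step 4: where the wider product window enters.** It lies after T3, so removing interval 1 leaves it in place. Any CCB variable built from 6.1, post-op CCB included, carries it.

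**Step 5: secondary endpoints.**
- The window label in 6.2 names intervals 1 and 2, but the words that explain it describe interval 2 alone. Protamine there is limited to 2b, which disagrees with 6.1.
- The product list in 6.2 leaves out fibrinogen concentrate and anti-fibrinolytics. Section 5.2 adopts the 5.1 definition, which includes both.
- Red cells are counted intra-operatively or during the CICU stay in 5.2, but in interval 2 from INNOVIAN alone in 6.2. Section 4.1 says INNOVIAN covers time in CICU, and that the CRF records red cells during the operation and up to CICU admission. Section 6.4 computes units from intra-operative, grey-area and INNOVIAN data.

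**The case against.** The strongest reply is that section 7.2 already protects the main models. Models 2C to 2E are set against post-op CCB only, and any CCB is kept for analyses in which interval 1 follows the predictor. A reader might infer from 6.1 that Models 2C to 2E lose their temporal order. The SAP does not show that; it shows that the protection rests on a label with no derivation. This part of the reply stands, and limits the point to the analyses and conditions named in Step 3.

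The scope before the sample is also narrow. Only therapeutic protamine reaches back to interval 1. Section 5.1 counts protamine only after initial heparin reversal, and 2.2 has the sample taken straight after reversal. Footnote 2 of 5.1 adds a notes review for patients who had protamine and no other non-RBC product. This suggests that few patients are affected, but the SAP gives no count.

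A reader might also infer that 6.1 brings in events days after the sample. That depends on a CICU stay the SAP does not report, and 5.1 itself admits late events through reoperation during the hospital stay. Aligning the treatment windows would not remove those.

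For the secondary endpoints, the stray interval label in 6.2 is contradicted within its own sentence and is a label error. A reader might conclude that red cells given between T3 and T4 are lost. Section 6.4 shows unit totals drawing on more than INNOVIAN, so the source column in 6.2 may merely be incomplete. Section 5.3, however, states that these data exist for the CICU admission only, so the sections still need reconciling.

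**Conclusion.** The contradiction is certain and lies in the primary outcome: 5.1 and 6.1 disagree on the window for products and on the window for protamine, and the two outcomes that 7.2 models have no derivation. It should be corrected before the results are relied on.

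The consequence is conditional. Pre-sample protamine becomes an outcome of the post-operative test if the 6.1 variable serves A1(b), A1(c) or 7.4.3, or if post-op CCB is built from it without removing interval 1. The longer product window affects post-op CCB in either case.

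No size is claimed. A fall in AUC could be produced by assuming an event rate, a true AUC and a share of late-only treatment, but the SAP supplies none of these. The direction of bias from pre-sample events is not established either. The 2b-only protamine rule in 6.2 suggests that 6.1 was simply not updated; that is inference.

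**What to change.** 1. Make the treatment window in 6.1 identical to 5.1: interval 2b for all early pro-haemostatic treatment, protamine included.
2. Derive two named variables in section 6. *Post-op CCB* counts only qualifying events after T3 and is used for every analysis of a post-operative test (Models 2C to 2E, A1, 7.4.3) and for Model 2B. *Any CCB* adds interval 1 events and is used only for the any-CCB baseline model and Model 2A. State in 5.1 which interval 1 events count, and state whether a patient with an interval 1 event is kept, excluded or counted as a non-case in the post-op CCB analyses.
3. In 6.2, drop interval 1 from the label for pro-haemostatic treatment so that it matches its own explanation, and use the 5.1 product list, adding fibrinogen concentrate and anti-fibrinolytics.
4. Reconcile the red-cell window and sources across 5.2, 6.2 and 6.4, naming the CRF as the source for T3 to T4 where its timing allows.

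The cost is SAP wording, recorded as an amendment, and a re-run of the derivation and the models that use it. INNOVIAN is hourly and the CRFs run to 12 hours after CICU transfer, so a cut at T6 can be programmed. The SAP does not say whether intra-operative products on the CRF are timed relative to T3; this should be checked first.

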6.2 Secondary endpoints

New variable	Rules	Data sources
RBC transfusion	Any RBC transfusion during interval 2	INNOVIAN clinical information

⁵ Diagnosis, evaluation, and management of acute kidney injury: a KDIGO summary (Part 1). Kellum *et al.* Critical Care 2013, 17:204

STATISTICAL ANALYSIS PLAN

COPTIC: Coagulation and platelet laboratory testing in cardiac surgery
A prognostic study of associations between post-operative test results and subsequent bleeding

New variable	Rules	Data sources
(binary)	(the time between post-operative samples are taken and discharge from CICU).	system
RBC >4 units (binary)	Any RBC transfusion >4 units during interval 2 (the time between post-operative samples are taken and discharge from CICU).	INNOVIAN clinical information system
Non-routine pro-haemostatic treatments (binary)	Any platelet, FFP, cryoprecipitate or rFVII transfusion during intervals 1 and 2 (the time between post-operative samples are taken and discharge from CICU), or therapeutic protamine during interval 2b (the time between post-operative samples are taken and 12 hours post CICU-admission).	INNOVIAN clinical information system and CRFs
Serious post-operative complications:		
Death (binary)	Vital status (alive vs. died in theatre OR died in hospital).	PATS Database (updated with NSTS data)
MI (binary)	Any MI occurring before discharge OR death from MI in hospital.	PATS Database, INNOVIAN clinical information system and death certificate data
Stroke (binary)	Any peri- OR post-operative neurological complication (stroke; transient ischaemic attack; hemiplegia; paralysis; paraplegia; dysphasia; cerebral/CNS infarct/embolus).	PATS Database, INNOVIAN clinical information system
AKI (binary)	Serum creatinine increased by ≥ 26.5 $\mu\text{mol/l}$ from the pre-operative value within 48 hours of surgery OR serum creatinine increased ≥ 1.5 times the pre-operative value within 7 days of surgery.	Creatinine data
Infection during hospital admission (binary)	Any infective complication (chest infection; wound infection; mediastinitis; graft site infection; sternal wound infection; urinary tract infection; septic; sepsis; blood borne infection).	PATS Database and INNOVIAN clinical information system

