3.2 Flow of participants

There is no study-specific follow-up for participants in the study, although clinical data extracted from the PATS database, which covers the period from admission for surgery until their date of discharge, will be used. Information collected prospectively on study subjects specifically for the study and recorded on case report forms (CRFs) relate to the period up until 12 hours after transfer to CICU.

The participant flow will be described via the flowchart (reference [Figure F1](#)).

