4. COPTIC DATA COLLECTION

4.1 Data sources

Information will be collected from the following sources:

Data sources and identification details for linkage

Data type	Brief description	Identification for linkage
CRF Data	Information on time samples were taken, time of CICU admission, blood loss 6 and 12 hours post CICU admission, red blood cells (RBC) and non-RBC transfusions during operation and post-	STUDYID (identifies patient), COPTIC SAMPLEID (identifies sample), operation date, Hospital number/BRI Trust number

STATISTICAL ANALYSIS PLAN

COPTIC: Coagulation and platelet laboratory testing in cardiac surgery
A prognostic study of associations between post-operative test results
and subsequent bleeding

Data type	Brief description	Identification for linkage
	operatively up to CICU admission.	
Clinical data	Data extract from PATS Database including reoperation details (Section 5.1 (iii) and clinical outcomes as detailed in Section 2.5 (c).	Hospital number/BRI Trust number, name, sex, date of birth, operation date
Clinical data	Data extract from INNOVIAN, clinical information system of hourly data for time spent in CICU. These data include red blood cells (RBC) and non-RBC transfusions during CICU admission and clinical outcomes as detailed in Section 2.5 (c).	Hospital number/BRI Trust number, operation date
Clinical data	Creatinine test results for all consenting COPTIC patients, restricted to the closest test prior to the operation (pre-op) and any tests after the operation but within 7 days of the operation date (post-op)	BRI Trust number, date of birth
Laboratory test results	Results from all laboratory tests detailed in Section 2.5.1. These are transferred from the coagulation lab as a single file (FBC) or in the form of many separate files of weekly results (Multiplate, TEG and ROTEM).	All post-operative samples are identified by the COPTIC SAMPLEID (as in CRF data). The date of test will also be used to aid linkage.

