COPTIC: Coagulation and platelet laboratory testing in cardiac surgery
A prognostic study of associations between post-operative test results
and subsequent bleeding

	MI STEMI NSTEMI ST elevation	Low cardiac output Cardiogenic shock IABP
Any stroke	Stroke Transient ischaemic attack, Hemiplegia Paralysis Paraplegia Dysphasia Cerebral/central nervous system (CNS) infarct/embolus	Loss of sensation CNS deficit Focal neurology Motor loss/deficit Sensation loss/deficit Brainstem Seizure Fit
Acute renal injury	Haemofiltration Haemodialysis Haemodiafiltration Dialysis Filtration Acute renal failure AKI Renal injury Kidney injury	New haemofiltration/dialysis CVVH RRT Already on dialysis
Sepsis	Chest infection Wound infection Mediastinitis Graft site infection Sternal wound infection Urinary tract infection Septic Sepsis Blood borne infection	Dehiscence Deep sternal wound Oozy sternum Positive blood culture Positive wound culture SIRS

Each of these secondary outcomes will be recorded as having occurred if there is evidence of a positive event within PATS or within INNOVIAN, including the review of free text.

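### The MI derivation has no new-onset or post-surgery condition, so an infarct that precedes surgery can be scored as a post-operative complication

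*SAP*

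**What the plan says.** Section 5.2 defines the outcome group as "Serious post-operative complications, i.e. death, myocardial infarction (MI), any stroke, acute kidney injury (AKI) and sepsis during hospital admission". In the derivation table of section 6.2, the MI row stands under the heading "Serious post-operative complications", and its rule reads "Any MI occurring before discharge OR death from MI in hospital".

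The sources are the PATS database, INNOVIAN and death certificates. By section 3.2, the PATS data "covers the period from admission for surgery until their date of discharge". Section 4.1 describes INNOVIAN as a "clinical information system of hourly data for time spent in CICU". INNOVIAN events are found first as recorded events and "secondly by an electronic review of the following five free text fields extracted from INNOVIAN". These fields are reviews, progress notes, problem entries and discharge plans. The MI search terms include MI, Infarct, STEMI and NSTEMI. The MI context terms describe the type of infarct or the haemodynamic state.

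On scoring, section 5.2 says: "Each of these secondary outcomes will be recorded as having occurred if there is evidence of a positive event within PATS". INNOVIAN is an equal alternative to PATS, and the reading of free text is included.

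**The concern.** Each place that could set the start of the MI window leaves it open. The hospital admission, the time before discharge and the PATS coverage all include inpatient days before the operation. Intensive-care notes are written after surgery, but they can mention an earlier infarct, and no search or context term separates a new event from an old one.

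MI is then used as an outcome in analysis A4 (section 7), where each secondary outcome is regressed on the post-operative test results and ROC thresholds are sought. Two things are at stake. Infarcts that precede the blood sample would inflate the MI count and dilute any real association. Also, if pre-operative infarction is commoner in patients on aspirin plus a P2Y₁₂ blocker, false events would concentrate where the platelet tests are low because of the drug. The SAP itself says, in section 2.3, that these drugs alter some of the tests. The link from infarct to dual therapy is an assumption; the SAP does not say why patients were on it.

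**Working it through.** **1. The rows side by side (section 6.2)**

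| Outcome | Start of window in the rule | New versus existing |
|---|---|---|
| Stroke | Yes: "Any peri- OR post-operative neurological complication" | Timing is part of the rule |
| AKI | Yes: creatinine rise within 48 hours or 7 days of surgery | Measured from the pre-operative value |
| MI | None; ends at discharge | Nothing stated |
| Infection | None; during admission | Nothing stated |

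MI is therefore not the only row without a start, but it lacks what stroke and AKI have. In the section 5.2 search table, the renal context terms at least mention new filtration or dialysis and patients already on dialysis. The MI context terms contain no comparable wording.

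**2. What size could this have?** The SAP states no MI rate or power for MI, so there is no figure to reproduce. What follows is an illustration.

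Inputs from the SAP: N = 2400 (section 3.1, the planned total, not the analysed number); about 25% on dual therapy (section 2.3).

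Assumptions: true post-operative MI risk t = 2%, the same in every drug group and unrelated to the test; false-hit probability f in dual-therapy patients and f/5 in the rest; platelet test 1 SD lower on dual therapy.

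Scored risk in a group = t + (1 − t) × f.

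For f = 5% and 1%:
- Dual therapy: 0.02 + 0.98 × 0.05 = 0.0690
- Rest: 0.02 + 0.98 × 0.01 = 0.0298
- Scored events: 2400 × (0.25 × 0.0690 + 0.75 × 0.0298) = 95.0, against 2400 × 0.02 = 48 true
- False share: (95.0 − 48)/95.0 = 49%
- Odds ratio, dual versus rest: (0.0690/0.9310)/(0.0298/0.9702) = 2.41, where the truth is 1

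The last column below comes from a logistic regression of scored MI on the test alone under these assumptions, with the approximate 95% interval that 2400 patients would give.

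| f dual / rest | Scored events | False share | OR dual v rest | OR per SD lower test, unadjusted |
|---|---|---|---|---|
| 2% / 0.4% | 66.8 | 28% | 1.68 | 1.10 (0.88 to 1.37) |
| 5% / 1% | 95.0 | 49% | 2.41 | 1.18 (0.97 to 1.42) |
| 10% / 2% | 142.1 | 66% | 3.24 | 1.25 (1.07 to 1.46) |

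Letting t run from 1% to 3% over the same three rows gives false shares from 21% to 80% and odds ratios per SD from 1.07 to 1.30.

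**3. Two checks on the mechanism**

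- Equal false hits. With f = 2% in everyone, the count is 2400 × (0.02 + 0.98 × 0.02) = 95.0 again, but both odds ratios are 1.00. The inflation needs only false hits; the spurious association also needs them to differ by drug group.
- Adjustment. Adding the dual-therapy indicator returns the test odds ratio to 1.00 in every row. This is by construction, because false hits here depend only on drug group.

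**4. Is that adjustment planned for MI?** Section 7.4.2 adjusts for the confounders of section 2.7. Those are age, sex, diabetes, type and urgency of surgery, kidney function and haematocrit, with platelet count in all models. Treatment group is not among them. It appears in the footnote to section 7.2, as a baseline covariate for the CCB models. Section 7.4.3 also reports unadjusted odds ratios.

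**The case against.** The strongest reply is that the intent is plain. The MI row sits under a heading that says post-operative, and section 5.2 uses the same label. Read with its heading, the rule means a post-operative MI before discharge. This stands as evidence of intent. It does not settle the derivation, because the stroke row under the same heading still states its timing and the MI row does not.

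A reader might infer that any text match on a term such as NSTEMI scores the outcome. The SAP does not say so: it asks for evidence of a positive event, refers to a review of the text and lists context terms. What it lacks is any statement of how context terms are applied, and none of those for MI concerns timing. Nor does it say that the renal terms cancel a hit; the AKI row uses creatinine data alone.

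The contents of the sources are unseen. The PATS field for MI may hold only post-operative complications, and the notes may seldom mention earlier infarcts. That stands, and it is why no rate can be given.

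On bias, the planned adjustment for urgency and type of surgery could absorb part of it, and treatment group could be added, since the list in section 2.7 need not be exhaustive. Two of the three illustrative intervals include 1. All of this stands. Adjustment would not, however, remove the false events themselves.

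**Conclusion.** The concern holds as a gap between label and rule. Followed literally, the MI derivation can score an infarct that precedes both the operation and the predictor, and nothing stated in section 5.2 filters it out. The certain consequence is that the MI count depends on unwritten judgement about timing. How many events are affected cannot be known from the SAP.

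A reader might go further and infer that the platelet test–MI results will be confounded by the indication for dual therapy. The document does not support that. It would need pre-operative infarction to be commoner in the dual-therapy group, those infarcts to pass the review, and a model without treatment group. Only the last can be partly checked: section 2.7 does not name treatment group. The figures of roughly 67 to 142 scored events against 48, and odds ratios of 1.10 to 1.25 per SD, rest on assumed rates.

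The reach is limited to one secondary outcome. CCB and the platform comparison built on it are untouched. The change is worth making because it is cheap and the present wording can give a wrong result.

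**What to change.** - **Section 6.2:** define MI as a new peri- or post-operative MI before discharge, or in-hospital death from such an MI. This matches the stroke row. Starting the window at the post-operative sample is less suitable: it would drop intra-operative MI and would need onset times that the SAP does not show to be available.
- **Section 5.2:** state that an MI hit in free text counts only if the text describes a new peri- or post-operative event, and that hits describing a previous MI or the indication for surgery are negative. Say how the context terms are used in that decision.
- **Review:** have flagged text read without knowledge of the laboratory results.

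The cost is a few lines of SAP wording, somewhat more reading of flagged notes, and fewer MI events for that model. Naming treatment group as a covariate in the MI model would be a useful addition, but it does not replace the new-onset condition.
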